6.1.3.14.1 Medical Outcomes Study 36-Item Short-Form Health Survey (SF-36)

The Medical Outcomes Study 36-Item Short-Form Health Survey (SF-36) is a multi-purpose, short-form health survey with 36 questions (see Appendix [10.1](#)). It yields an 8-scale profile of functional health and well-being scores as well as psychometrically-based physical and mental health summary measures. It is a generic measure, as opposed to one that targets a specific age, disease, or treatment group. Accordingly, the SF-36 has proven useful in surveys of general and specific populations, comparing the relative burden of diseases, and in differentiating the health benefits produced by a wide range of different treatments.

The SF-36 contains 36 items that measure eight dimensions or scales: (1) physical functioning (PF); (2) role limitations due to physical health problems (RP); (3) bodily pain (BP); (4) social functioning (SF); (5) general health perceptions (GH); (6) role limitations due to emotional problems (RE); (7) vitality, energy or fatigue (VT); and (8) mental health (MH) (see Appendix [10.1](#)). In addition, two summary measures, defined as the Physical Component Score (SF-36 PCS) and Mental Component Score (SF-36 MCS) will be provided.

Scoring of each dimension and the summary measure will be performed by QualyMetric using QualityMetric Health Outcomes(tm) Scoring Software 4.5.

Change from baseline to the average value in weeks 12-28 will be calculated for the Physical Component Scores of SF-36 (SF-36 PCS), following the same rules as defined in Section [6.1.2.5](#)

For missing SF-36 PCS values, refer to Section [7.11.1](#) imputation rules. Baseline always refers to the assessment at day 1 to be performed prior to first study drug administration.

The number and percent of subjects with an increase from baseline of $<3 / \geq 3$ points and of $<5 / \geq 5$ points will be calculated for each visit for the following: Vitality Score (SF-36 VT), Physical Functioning score (SF-36 PF) and Physical Component score (SF-36 PCS).

In addition, the eight dimensions and the two summary measures and their associated change from baseline will be reported by visit.

6.1.3.14.2 Functional Assessment of Cancer Therapy –Anemia (FACT-An)

The Functional Assessment of Cancer Therapy – General (FACT-G; version 4) contains 27 items that cover four dimensions of well-being: physical (PWB) – 7 items, functional (FWB) – 7 items, social/family (SWB) – 7 items, and emotional (EWB) – 6 items.

The ‘additional concerns’ section contains 20 items: 13 fatigue specific items plus 7 additional items related to anemia were developed for use in conjunction with the FACT-G (Cella 1997). The 13 fatigue items plus the seven additional items related to anemia comprise the Anemia Subscale (AnS). Administration of the FACT-G plus the Anemia Subscale (AnS) is referred to as the FACT-An. The FACT-An has a recall period of the ‘past seven days’. Respondents are asked to provide responses, (i.e., ‘Not at all’, ‘A little bit’, ‘Somewhat’, ‘Quite a bit’ and ‘Very much’), to a list of statements which are either positively or negatively phrased. A final higher score indicates better QoL (see Appendix [10.2](#)).

Each individual item is scored from 0 (Not at all) to 4 (Very much), and then the total score is obtained by summation of the resulted scores.

If there are missing items, subscale scores can be standardized. This is done by multiplying the sum of the subscale by the number of items in the subscale, then dividing by the number of items actually answered. This can be done on the scoring guide or by using the formula below:

Prorated subscale score = [Sum of item scores] x [N of items in subscale] / [N of items answered]

When there are missing data, standardizing by subscale in this way is acceptable (Webster 2003) as long as more than 50% of the items were answered (e.g., a minimum of 4 of 7 items, 4 of 6 items, etc). The total score is then calculated as the sum of the un-weighted subscale scores. The FACT scale is considered to be an acceptable indicator of a subject's quality of life as long as overall item response rate is greater than 80% (e.g., at least 22 of 27 FACT-G items completed). This is not to be confused with individual subscale item response rate, which allows a subscale score to be prorated for missing items if greater than 50% of items are answered. In addition, a total score should only be calculated if ALL of the component subscales have available scores.

The FACT-An instrument will be scored according to Appendix [10.2](#) The following 9 scores will be calculated:

- PWB subscale score
- SWB subscale score
- EWB subscale score
- FWB subscale score
- AnS subscale score
- FACT-An TOI score
- FACT-G total score
- FACT-An total score
- Fatigue subscale score

Change from baseline to the average value in weeks 12-28 will be reported for the two scores (Anemia subscale 'Additional concerns' of FACT-An score and Total FACT-AN score). In addition, the score and change from baseline will be reported for each visit for all six scores.

Change from baseline to the average value in weeks 12-28 will be calculated for the FACT-An subscore, following the same rules as defined in Section [6.1.2.4](#)

No imputation will be performed in case of a missing value.

Baseline always refers to the assessment at day 1 to be performed prior to first study drug administration.

6.1.3.14.3 EQ-5D 5L

The EQ-5D 5L is an international standardized non-disease specific (i.e., generic) instrument for describing and valuing health status, and a multi-dimensional measure of health-related QoL (see Appendix [10.3](#)).

It includes two main components: (1) a VAS scale rating perception of overall health and (2) 5 qualitative domains: Mobility, Self-Care, Usual Activities, Pain/Discomfort, and Anxiety/Depression. For more details and description of the questionnaire, refer to Appendix [10.3](#)

Change from baseline to the average value in weeks 12-28 will be calculated for the EQ 5D 5L VAS, following the same rules as defined in Section [6.1.2.4](#)

Frequency distributions will be described for each visit for:

- EQ-5D 5L Mobility Score
- EQ-5D 5L Self-Care Score
- EQ-5D 5L Usual Activities Score
- EQ-5D 5L Pain/Discomfort Score
- EQ-5D 5L Anxiety/Depression Score

The evaluation period for the VAS score is defined as the average of available EQ-5D 5L VAS scores of weeks 12-28 (visit at W12 and W28).

No imputation will be performed in case of a missing item. Baseline always refers to the assessment at day 1 to be performed prior to first study drug administration.

6.1.3.14.4 Work Productivity and Activity Impairment (WPAI: ANS)

The objective of the Work Productivity and Activity Impairment questionnaire: Anemic Symptoms v2 (WPAI: ANS) is to measure work and activity impairment during the past seven days due to anemia. It is self-assessed. The WPAI: ANS consists of 6 questions, including asking if the subject is working, how many hours the person missed work due to anemic symptoms, how many hours the subject actually worked and how the anemic symptoms impacted the productivity and ability to do daily activities (see Appendix [10.4](#)).

For subjects who are currently employed, the following four items will be calculated:

- Percent work time missed due to anaemic symptoms: $100 \times Q2 / (Q2 + Q4)$
- Percent impairment while working due to anaemic symptoms: $100 \times Q5 / 10$
- Percent overall work impairment due to anaemic symptoms: $100 \times Q2 / (Q2 + Q4) + [(1 - Q2 / (Q2 + Q4)) \times (Q5 / 10)]$
- Percent activity impairment due to anaemic symptoms: $100 \times Q6 / 10$

Change from baseline to the average value in weeks 12-28 and in weeks 36-52 will be calculated for these items, following the same rules as defined in Section [6.1.2.4](#) The evaluation period score is defined as the average of available WPAI: ANS subscore of weeks 12-28 (visit at W12 and W28) and weeks 36-52 (visit at W36 and W52).

No imputation will be performed in case of a missing item. Baseline always refers to the assessment at day 1 to be performed prior to first study drug administration.

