10.4 Appendix 4: WPAI:ANS V2.0

The following questions ask about the effect of your anaemic symptoms on your ability to work and perform normal daily activities. *Please fill in the blanks or circle a number, as indicated.*

1. Are you currently employed (working for pay)? _____ NO _____ YES
If NO, tick "NO" and skip to question 6.

The next questions refer to the **past seven days**, not including today.

2. During the past seven days, how many hours did you miss from work because of problems associated with your anaemic symptoms? *Include hours you missed on sick days, times you went in late, left early, etc., because of your anaemic symptoms . Do not include time you missed to participate in this study.*

_____ HOURS

3. During the past seven days, how many hours did you miss from work because of any other reason, such as annual leave, holidays, time off to participate in this study?

_____ HOURS

4. During the past seven days, how many hours did you actually work?

_____ HOURS (If "0", skip to question 6)

[figure not shown]
5. During the past seven days, how much did your anaemic symptoms affect your productivity while you were working?

Think about days you were limited in the amount or kind of work you could do, days you accomplished less than you would like, or days you could not do your work as carefully as usual.

If anaemic symptoms affected your work only a little, choose a low number. Choose a high number if anaemic symptoms affected your work a great deal.

WPAI:ANS

Consider only how much anaemic symptoms affected productivity while you were working.

[figure not shown]

CIRCLE A NUMBER

6. During the past seven days, how much did your anaemic symptoms affect your ability to perform your normal daily activities, other than work at a job?

By normal activities, we mean the usual activities you perform, such as working around the house, shopping, childcare, exercising, studying, etc. Think about times you were limited in the amount or kind of activities you could perform and times you accomplished less than you would like. If anaemic symptoms affected your activities only a little, choose a low number. Choose a high number if anaemic symptoms affected your activities a great deal.

Consider only how much anaemic symptoms affected your ability to do your normal daily activities, other than work at a job.

CIRCLE A NUMBER

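### The WPAI overall work impairment formula multiplies only its first term by 100, and activity impairment is derived only for employed subjects although non-employed subjects also answer that item

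*SAP*

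**What the plan says.** SAP 6.1.3.14.4 opens its scoring rules with "For subjects who are currently employed, the following four items will be calculated" and then lists:

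- "Percent work time missed due to anaemic symptoms": 100 × Q2/(Q2+Q4)
- "Percent impairment while working due to anaemic symptoms": 100 × Q5/10
- "Percent overall work impairment due to anaemic symptoms": 100 × Q2/(Q2+Q4) + [(1 − Q2/(Q2+Q4)) × (Q5/10)]
- "Percent activity impairment due to anaemic symptoms": 100 × Q6/10

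Q2 is hours missed because of anaemic symptoms, Q4 is hours actually worked, and Q5 and Q6 are 0–10 ratings. The questionnaire (SAP Appendix 4, also protocol Appendix 9) tells a subject who is not employed to answer no at question 1 "and skip to question 6". Question 6 asks how far anaemic symptoms "affect your ability to perform your normal daily activities, other than work at a job".

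SAP 7.4.3.14 summarizes the derived WPAI variables by visit and arm, with changes from baseline to weeks 12–28 and 36–52. It restates neither the formula nor the population.

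**The concern.** There are two separate faults in one short section.

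**Scaling.** The overall score is meant to combine time lost with impairment during the time worked. As printed, it adds a percentage to a fraction. The other three items are all on a 0–100 scale, and the stand-alone Q5 item does carry the factor of 100. The printed overall score is therefore little more than a second copy of work time missed, with on-the-job impairment almost absent.

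**Population.** Protocol 5.3.3.1.5 describes WPAI:ANS as covering two domains, work and daily activities. The activity item uses Q6 alone and needs no information about a job. Under the employed-only lead-in, every non-employed subject is missing from the activity summaries. A subject who stops or starts work also leaves or enters them, so the denominator moves with employment status for an item that has nothing to do with employment.

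**Working it through.** The documents give no numerical WPAI result, so there is no stated figure to reproduce. The check evaluates the formula as printed and compares it with the version in which 100 multiplies the whole sum.

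**Notation.** Let m = Q2/(Q2+Q4), the share of hours missed, and q = Q5/10.

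- Printed: 100m + (1 − m)q
- Whole sum scaled: 100[m + (1 − m)q]
- Difference: 100(1 − m)q − (1 − m)q = 99(1 − m)q

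The printed second term, (1 − m)q, cannot exceed 1. The difference is largest at m = 0 and q = 1, where it is 99 points. It vanishes when Q5 = 0.

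**Worked cases.** The answers are assumed for illustration (hours summing to 40); the documents give no distribution.

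| Q2 | Q4 | Q5 | Work time missed | Impairment while working | Overall, printed | Overall, scaled | Difference |
|---|---|---|---|---|---|---|---|
| 0 | 40 | 5 | 0 | 50 | 0.5 | 50 | 49.5 |
| 4 | 36 | 3 | 10 | 30 | 10.27 | 37 | 26.73 |
| 8 | 32 | 6 | 20 | 60 | 20.48 | 68 | 47.52 |
| 0 | 40 | 10 | 0 | 100 | 1 | 100 | 99 |

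Third row in full: m = 8/40 = 0.2 and q = 0.6. Printed: 100 × 0.2 + 0.8 × 0.6 = 20 + 0.48 = 20.48. Scaled: 100 × (0.2 + 0.48) = 68.

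**Internal check.** In the scaled version the overall score is never below either component. In all four rows the printed score is below impairment while working as the SAP itself defines it; in the first row it is 0.5% against 50%. A combined score cannot sensibly behave that way.

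**Population.** Set side by side:

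1. The lead-in in SAP 6.1.3.14.4 restricts all four items to employed subjects.
2. Three of the four items use Q2, Q4 or Q5, which non-employed subjects skip. For these the restriction is necessary.
3. The fourth uses only Q6, which non-employed subjects are told to answer and which excludes paid work by its wording. For this item the restriction removes valid answers.

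The documents do not state the share of non-employed subjects, so the size of this loss cannot be calculated.

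**The case against.** **Weight.** WPAI appears in SAP Table 5 as part of additional secondary endpoint 14, but protocol 5.4.6 lists it as exploratory and the SAP analyses it descriptively. It is outside the fixed sequence, and no test, alpha or power depends on it. This stands and limits the consequence, but the score is still wrong as specified.

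**Data are not lost.** SAP 7.1 lists all collected eCRF data apart from the physical examination, so Q6 answers from non-employed subjects would appear in listings. The two work components are also reported separately on the right scale, and SAP 7.4.3.14 reports the number employed at each visit. This stands as well: the loss is from the summaries, not from the record.

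**Extraction artefact or programming fix.** An outer bracket might have been lost in conversion from PDF, or a programmer might apply usual scoring. The printed brackets balance and nothing in the text points to a lost symbol. SAP 6.1.3.14 mentions an external vendor for some derivations, but the SAP assigns vendor scoring only to SF-36. Appendix 4 gives the WPAI questionnaire without scoring rules, so 6.1.3.14.4 is the only specification. SAP section 1 requires changes from the planned analyses to be justified in the study report, so a silent correction would be an undocumented departure.

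**Remaining gaps.** Employed subjects with Q4 = 0 skip Q5, and Q2 + Q4 = 0 leaves the ratio undefined. Neither case is settled by rescaling. This is a fair but separate point that does not make the correction unsound.

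**Conclusion.** Both parts hold on the documents' own text. The overall work impairment score as printed is too low by 99(1 − m)q points, up to 99, whenever a subject reports any impairment during hours worked. The activity score is confined to employed subjects without reason, since Q6 is asked of everyone who completes the form.

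The scaling result rests only on the printed formula; the individual examples rest on assumed answers. The effect on any difference between arms is unknown, because the documents give neither a distribution of responses nor an employment rate. The damage is limited to two of four WPAI variables, all descriptive. It should be corrected, but it does not bear on the trial's main conclusions.

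**What to change.** In SAP 6.1.3.14.4:

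1. Replace the overall work impairment formula with 100 × {Q2/(Q2+Q4) + [1 − Q2/(Q2+Q4)] × (Q5/10)}.
2. Restrict the employed-only lead-in to the three work items, and state that activity impairment, 100 × Q6/10, is computed for every subject who answers Q6.

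The cost is one bracket and one sentence, with matching changes to the derivation program and the table denominators. No new data are needed. The same edit is a convenient place to state how overall impairment is handled when Q4 = 0 or Q2 + Q4 = 0.

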6.1.3.15 Patients' Global Impression of Change (PGIC)

The Patients' Global Impression of Change (PGIC) is a subject-rated instrument that measures change in subjects' overall status since the start of the study on a 7-point qualitative scale ranging from 1 (very much improved) to 7 (very much worse) (see Appendix 10.5).

Data will be reported qualitatively by assessment as follows:

- Reported subject status,
- Combined Categories as binary:
 - Very Much Improved + Much Improved (yes/no)
 - Very Much Improved + Much Improved + Minimally Improved (yes/no)

No imputations will be performed in case of a missing item.

6.1.3.16 Hepcidin and Iron, HbA1c and CKD progression parameters

Changes from baseline to each study visit (see analysis windows in Table 31, Section 7.11.4) will be calculated for these parameters:

1. Serum hepcidin
2. Serum ferritin
3. Serum Iron
4. TSAT
5. HbA1c level
6. Fasting blood glucose
7. Serum creatinine (log transformed)
8. Albumin/creatinine ratio in urine (log transformed)

Serum creatinine and albumin/creatinine ratio in urine will be log transformed and any assessment occurring after the initiation of any dialysis (acute or chronic) will be excluded for the summaries.

For all variables above, baseline assessment is the assessment from Day 1 visit. If this value is missing, then the screening period value, if collected for that parameter, will be used.

CKD Progression variables:

- Time to CKD progression (composite of doubling serum creatinine, chronic dialysis or renal transplant, and Death)

First occurrence of serum creatinine being doubled compared with baseline during the Safety Emergent Period (see Section 6.2) will be calculated.

Occurrence of chronic dialysis or renal transplant (whichever occurring first) during the Safety Emergent Period (see Section 6.2) will be calculated.

Time to occurrence for a subject who died during the Safety Emergent Period (see Section 6.2) will be calculated.

For a subject, the time to CKD progression will be calculated (in years) as:

$$(\text{First event date} - \text{Analysis date of first dose intake} + 1) / 365.25$$

With 'First event date' defined as 'First occurrence of serum creatinine being doubled compared with baseline, first occurrence of chronic dialysis or renal transplant, occurrence of subject who died (whichever occurring first)' and 'Analysis date of first dose intake' defined in Section 6.5.4

For a subject without event, the time to censoring will be calculated (in years) as:

$$(\text{End of Safety Emergent Period} - \text{Analysis date of first dose intake} + 1) / 365.25$$

With 'Analysis date of first dose intake' defined in Section 6.5.4

- Time to chronic dialysis or renal transplant or occurrence for a subject who died Occurrence of chronic dialysis or renal transplant (whichever occurring first) during the Safety Emergent Period (see Section 6.2) will be calculated.

Time to occurrence for a subject who died during the Safety Emergent Period (see Section 6.2) will be calculated.

For a subject, the time to chronic dialysis or renal transplant or occurrence for a subject who died will be calculated (in years) as:

$$(\text{First event date} - \text{Analysis date of first dose intake} + 1) / 365.25$$

With 'First event date' defined as 'first occurrence of chronic dialysis or renal transplant, occurrence of subject who died (whichever occurring first)' and 'Analysis date of first dose intake' defined in Section 6.5.4

For a subject without event, the time to censoring will be calculated (in years) as:

$$(\text{End of Safety Emergent Period} - \text{Analysis date of first dose intake} + 1) / 365.25$$

With 'Analysis date of first dose intake' defined in Section 6.5.4

- Time to doubling of serum creatinine
First occurrence of serum creatinine being doubled compared with baseline during the Safety Emergent Period (see Section 6.2) will be calculated:

$$(\text{First event date} - \text{Analysis date of first dose intake} + 1) / 365.25$$

For a subject without event, the time to censoring will be calculated (in years) as:

$$(\text{End of Safety Emergent Period} - \text{Analysis date of first dose intake} + 1) / 365.25$$

With 'Analysis date of first dose intake' defined in Section 6.5.4

- Time to doubling of serum creatinine or chronic dialysis or renal transplant:
First occurrence of serum creatinine being doubled compared with baseline during the Safety Emergent Period (see Section 6.2) will be calculated. In addition, first occurrence of chronic dialysis or renal transplant during the Safety Emergent Period will be derived.

The endpoint is defined as time to doubling serum creatinine or chronic dialysis or renal transplant what ever comes first:

$(\text{First event date} - \text{Analysis date of first dose intake} + 1) / 365.25$

For a subject without event, the time to censoring will be calculated (in years) as:

$(\text{End of Safety Emergent Period} - \text{Analysis date of first dose intake} + 1) / 365.25$

With 'Analysis date of first dose intake' defined in Section 6.5.4

- Time to chronic dialysis or renal transplant:

Occurrence of chronic dialysis or renal transplant (whichever occurring first) during the Safety Emergent Period (see Section 6.2) will be calculated and time to event in years will be defined as :

$(\text{First event date} - \text{Analysis date of first dose intake}) / 365.25$

With 'First event date' defined as 'Date of dialysis or Date of renal transplant (whichever occurring first)' and 'Analysis date of first dose intake' defined in Section 6.5.4

For a subject without dialysis or transplant, the time to censoring will be calculated as:

$(\text{Date of End of Safety Emergent Period} - \text{Analysis date of first dose intake} + 1) / 365.25$

With Date of End of Safety Emergent Period defined in Section 7.11.5

- Occurrence of End Stage Renal Disease is taken directly from the eCRF with the following categories: f the following:
 - Underwent >30 days of dialysis therapy
 - Received kidney transplant
 - Planned kidney transplant
 - Physician recommended renal replacement therapy and subject refused therapy
 - Began dialysis and died < 30 days later
- ESRD-free survival is defined as time form first dose alive and not progressed to ESRD. The time to event will be derived where event is death or ESRD whatever is first.

The time to event will be derived (in years) as:

$(\text{Date of event} - \text{Analysis date of first dose intake} + 1) / 365.25$

where 'date of event' is defined as date of occurrence of End Stage Renal Disease (recorded End Stage Renal Disease as AE) or date of death, whichever comes first, during the Safety Emergent Period.

For a subject without event, the time to censoring will be calculated (in years) as:

$(\text{End of Safety Emergent Period} - \text{Analysis date of first dose intake} + 1) / 365.25$

- Proportion and Time to at least a 40% eGFR decrease from baseline, based on all eGFR values before start of acute or chronic dialysis

Time to at least 40% decrease in eGFR from baseline, chronic dialysis or renal transplant:

First occurrence of at least 40% decrease in eGFR from baseline during the Safety Emergent Period (see Section 6.2) will be calculated.

Occurrence of chronic dialysis or renal transplant (whichever occurring first) during the Safety Emergent Period (see Section 6.2) will be calculated.

For a subject, the time to at least 40% decrease in eGFR from baseline, chronic dialysis or renal transplant will be calculated (in years) as:

$$(\text{First event date} - \text{Analysis date of first dose intake} + 1) / 365.25$$

With 'First event date' defined as 'First occurrence of 40% decrease in eGFR from baseline, first occurrence of chronic dialysis or renal transplant (whichever occurring first) and 'Analysis date of first dose intake' defined in Section 6.5.4

For a subject without event, the time to censoring will be calculated (in years) as:

$$(\text{End of Safety Emergent Period} - \text{Analysis date of first dose intake} + 1) / 365.25$$

With 'Analysis date of first dose intake' defined in Section 6.5.4

- Time to at least 40% decrease in eGFR from baseline

First occurrence of at least 40% decrease in eGFR from baseline during the Safety Emergent Period (see Section 6.2) will be calculated.

For a subject, the time to at least 40% decrease in eGFR from baseline will be calculated (in years) as:

$$(\text{First event date} - \text{Analysis date of first dose intake} + 1) / 365.25$$

With 'First event date' defined as 'First occurrence of 40% decrease in eGFR from baseline, and 'Analysis date of first dose intake' defined in Section 6.5.4

For a subject without event, the time to censoring will be calculated (in years) as:

$$(\min[\text{End of Safety Emergent Period, first occurrence of chronic dialysis date}] - \text{Analysis date of first dose intake} + 1) / 365.25$$

With 'Analysis date of first dose intake' defined in Section 6.5.4

6.1.4 Other exploratory variables: hs-CRP (High Sensitivity C-Reactive Protein) and sTFR (Soluble Transferrin Receptor)

The variables hs-CRP and sTFR will be collected from the central laboratory on the following visits: Day 1, weeks 4, 12, 20, 36, 52, EOT and EOS. Absolute values and changes from baseline to each study visit will be calculated. Baseline assessment is the assessment from Day 1 visit. If Day 1 assessment is missing, change from baseline will not be reported. Analysis windows are defined in Table 31, Section 7.11.4

